3. OBJECTIVE(S) AND ENDPOINT(S)

Objectives	Endpoints
Primary	

 To evaluate the efficacy of albiglutide liquid product as measured by glycated hemoglobin (HbA_{1c}) change from baseline at Week 26. 	
 Change from baseline in HbA_{1c} at Week 26
Secondary	

 To assess safety and tolerability of albiglutide specifically immunogenicity and ISRs. 	
 Adverse events (AEs) and serious AEs (SAEs), physical examinations, clinical laboratory evaluations, vital signs, and 12-lead electrocardiograms (ECGs). Anti-albiglutide antibody production and rates of ISRs over time.

 To evaluate the PD effect of albiglutide on fasting plasma glucose (FPG) change from baseline at Week 26. 	
 Change from baseline in FPG at Week 26

 To assess the PD effect of albiglutide over time 	
 Change from baseline in HbA_{1c} over time Change from baseline in FPG over time

 To evaluate trough PK concentrations of albiglutide following repeat dosing 	
 Trough concentrations of albiglutide

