9.4.2. Secondary Analyses

The evaluation of the safety and tolerability as assessed by immunogenicity and ISRs of albiglutide liquid drug product and the lyophilized drug product will be provided by reporting the event rates, and the associated 95% CI.

The overall general safety and tolerability of albiglutide liquid drug product versus lyophilized drug product will be evaluated in tabular and/or graphical format and summarized descriptively.

AEs and SAEs, physical examinations, clinical laboratory evaluations, vital sign measurements, and 12-lead electrocardiogram will be summarized by treatment group. For continuous variables, these summaries will include sample size, mean, median, standard deviation (and/or standard error), minimum, and maximum. For categorical variables, the summaries will include frequencies and corresponding percentages. The exposure-adjusted incidence rate will also be calculated as the number of events in a given period divided by the total person time on treatment of subjects at risk within the same period. The exposure-adjusted incidence rate will be expressed as an annualized rate expected. No inferential testing will be performed on the safety variables. Hypoglycemic events will be analyzed separately from other AEs. All hypoglycemic events will be classified as severe, documented symptomatic, asymptomatic, probable symptomatic, and pseudohypoglycemia, as defined in Section 7.4.9.

AEs will be coded using MedDRA. AEs will be summarized in various subsets, including on therapy AEs, related AEs, AEs leading to treatment discontinuation or withdrawal from study, SAEs, fatal AEs, etc. AEs will also be summarized by maximum intensity (mild, moderate, and severe).

Anti-albiglutide antibody results will be summarized by treatment group. In addition, the number and percentage of subjects with positive results along with the antibody titer values will be provided by visit.

The secondary endpoint FPG change from baseline at Week 26 will be analyzed using MMRM without imputation.

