
Secondary Analyses
	
 • The evaluation of the safety and tolerability as assessed by immunogenicity and ISRs of abiglutide liquid drug product and the lyophilized drug product will be provided by reporting the event rates, and the associated 95% CI. • The overall general safety and tolerability of abiglutide liquid drug product versus lyophilized drug product will be evaluated in tabular and/or graphical format and summarized descriptively. • The secondary endpoint Fasting Plasma Glucose (FPG) change from baseline at Week 26 will be analyzed using MMRM without imputation. • To assess the PD effect of abiglutide over time for the secondary endpoints change from baseline in HbA1c and in FPG over time; MMRM models without imputation will be used. • Pharmacokinetics (PK) trough plasma concentration data will be summarized by treatment. No formal statistical analyses will be conducted.

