6.6. Treatment Compliance

Study treatment (both active drug and placebo injector) will be administered to the subject by the site personnel in the clinic at each scheduled weekly visit from Week 0 (i.e. Baseline/Randomization), Week 1 through Week 25. At each scheduled weekly visit, study treatment administration status (Yes/No), date/time of dose administered (if Yes) and reason no dose administered (if No) will be recorded in the Exposure eCRF page.

Treatment compliance (in percentage) will be based on the Exposure eCRF page and calculated as total number of doses administered divided by total number of doses expected over all available scheduled visits on treatment. Treatment compliance will be summarized for all subjects, as well as for subjects who discontinue study treatment early and subjects who complete study treatment. Treatment compliance will be also categorized as < 80% and \geq 80%, and summarized descriptively by treatment group.

Individual subject compliance information will also be listed. All summaries will be performed using the safety population.

Acceptable overall compliance for IP (albiglutide liquid and lyophilized) in this study will be \geq 80%.

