8.2.2. Injection Site Reactions

Injection site reactions are reported by the investigators on the eCRF. The number and percentage of subjects with injection site reactions and 95% confidence intervals of the proportions will be presented by treatment group. In addition, the time to first occurrence of an injection site reaction will be analyzed and presented in a manner identical to that described for the first occurrence of a GI event in Section 8.2.7.5.

The number and percentage of subjects reporting injection site reactions at each study week will be presented by treatment group. Each week will include those subjects with the onset of an injection site reaction during that particular week as well as those subjects with injection site reactions from previous weeks that have not resolved. The incidence of injection site reactions will be plotted over time. Various characteristics of injection site reactions at the event level and subject level will be summarized.

A by-subject listing of injection site reactions will also be produced.

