8.2.7. Adverse Events of Special Interest

For selected AEs of special interest such as hypoglycemia, the exposure-adjusted event rate, i.e., AE density, will be calculated as the number of events in a given period divided by the total person time on treatment of subjects at risk within the same period; the exposure-adjusted incidence rate will also be calculated as the number of subjects in a given period divided by the total person time on treatment of subjects at risk within the same period. The exposure-adjusted event rate and incidence rate will be expressed as an annualized rate (expected number of events or subjects per 100 person-years).

For any AEs of special interest, summary tables and by subject data listings will be provided.

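### In SAP 8.2.2 the only injection-site-reaction estimate with a stated confidence interval is the proportion of subjects with any reaction; no event rate with an interval is specified, although the protocol and the SAP synopsis commit to event rates.

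*SAP*

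**What the plan says.** Protocol 9.4.2, like the protocol synopsis, says that the evaluation of immunogenicity and ISRs "will be provided by reporting the event rates, and the associated 95% CI". The SAP synopsis repeats that it will be "provided by reporting the event rates, and the associated 95% CI". The matching secondary endpoint, in Protocol 3 and again in SAP 2.2, is "Anti-albiglutide antibody production and rates of ISRs over time".

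SAP 8.2.2 then lists the ISR outputs:

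- An overall subject-level summary: "The number and percentage of subjects with injection site reactions and 95% confidence intervals of the proportions will be presented by treatment group".
- Time to first reaction, handled as for GI events in 8.2.7.5 (median and Kaplan-Meier probabilities). No interval is stated.
- A weekly summary: "The number and percentage of subjects reporting injection site reactions at each study week will be presented by treatment group". It counts new and unresolved reactions and is plotted. No interval is stated.
- A descriptive summary: "Various characteristics of injection site reactions at the event level and subject level will be summarized". No rate and no interval is stated.
- A listing.

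The display list follows this structure (Tables 3.141 to 3.144, Figure 3.21) and has no table titled as an ISR event rate.

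Elsewhere, SAP 8.2.7 says: "For selected AEs of special interest such as hypoglycemia, the exposure-adjusted event rate, i.e., AE density, will be calculated". Section 11.5.4 defines that density as events divided by person-time on treatment. ISRs are not named there, no interval is mentioned, and 8.2.2 does not refer to it. SAP 2.1, which lists departures from the protocol's analysis plan, is silent on ISRs.

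**The concern.** A reaction can recur at any weekly dosing visit, and SAP 6.6 confirms that each visit involves two injectors: "Study treatment (both active drug and placebo injector) will be administered to the subject by the site personnel in the clinic". A proportion of subjects with any reaction, and a time to first reaction, both stop counting after the first event. Neither takes account of how many doses a subject received, and Protocol Table 2 reports that ISRs were the most common reason for withdrawal of study medication in the earlier program (about 2.0%). Two arms with the same number of reactors but different numbers of reactions would therefore have the same interval-bearing estimate.

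What is at stake is how precisely the report can describe a secondary outcome that the study rationale singles out. There is also a textual mismatch. The protocol and the SAP synopsis use one term, and the operative SAP section delivers something that may or may not be what the term means.

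**Working it through.** The documents give no precision or sample-size figure for ISRs, so there is none to reproduce. The check compares how the planned estimate and an event rate respond to recurrence.

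**Inputs from the documents**

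- Dosing visits: Week 0 to Week 25, so 26, with two injectors at each (SAP 6.6).
- Arm size: about 150 (Protocol 9.2.1).
- Subjects with at least one ISR on the lyophilized product: 41% if antibody positive, 14% if antibody negative (Protocol Table 2).
- Antibody incidence: 4.4% (Protocol 2.1) or about 5% (Protocol Table 2).
- Person-time: last dose minus first dose plus 26 days, divided by 365.25 (SAP 11.5.3).

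**Assumptions**

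- The 41% and 14% come from Phase III studies lasting 32 weeks to 3 years, with a different injection schedule. Applying them to 26 weeks here is an assumption.
- Reactions per affected subject: no figure is given, so a range of 1 to 8 is shown.
- All subjects are fully exposed.

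**Step 1. Exposure.** 26 × 2 = 52 injections per fully dosed subject. Person-time per subject is (175 + 26)/365.25 = 0.550 years. For 150 subjects this is 82.5 person-years, or 150 × 26 = 3,900 dosing visits.

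**Step 2. Expected proportion.** 0.044 × 41% + 0.956 × 14% = 15.2% (15.4% with 5% antibody positive), or about 23 of 150. The exact 95% CI for 23/150 = 15.3% is 10.0% to 22.1%. SAP 8.2.2 does not name its interval method; the exact binomial is used here, as in SAP 8.2.3.

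**Step 3. Event rate with the same 23 reactors.** Rate = 23 × m / 82.5 × 100, where m is reactions per affected subject. If every affected subject has m reactions, the standard error of the log rate is √[(1 − p)/(150p)] with p = 23/150. That is √(0.8467/23) = 0.192, and the clustered limits are the rate divided and multiplied by exp(1.96 × 0.192) = 1.46.

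| m (assumed) | Subject proportion (95% CI) | Events per 100 person-years | Poisson 95% CI | 95% CI allowing for clustering |
|---|---|---|---|---|
| 1 | 15.3% (10.0 to 22.1) | 27.9 | 17.7 to 41.8 | 19.1 to 40.6 |
| 2 | 15.3% (10.0 to 22.1) | 55.7 | 40.8 to 74.3 | 38.3 to 81.2 |
| 4 | 15.3% (10.0 to 22.1) | 111.5 | 89.8 to 136.7 | 76.5 to 162.3 |
| 8 | 15.3% (10.0 to 22.1) | 222.9 | 191.9 to 257.5 | 153.0 to 324.7 |

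If counts among affected subjects vary (geometric distribution), the clustered interval at m = 8 widens to 130.4 to 381.1. A Poisson interval would be too narrow once reactions repeat.

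**Step 4. Two-arm illustration (assumed).** Take 23 reactors in each arm, averaging 1.5 reactions on one product and 5 on the other. That is 23 × 1.5 ≈ 35 events against 23 × 5 = 115. Both arms show 15.3% (10.0 to 22.1), while the event counts differ by 115/35 ≈ 3.3-fold.

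**Step 5. What the weekly display would show.** If each event falls in its own subject-week, the average weekly percentages in Step 4 are 35/3,900 = 0.9% and 115/3,900 = 2.9%. The gap would be visible, without an interval.

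**The case against.** The strongest reply is that nothing has been broken. The protocol sentence covers immunogenicity and ISRs together. The SAP delivers immunogenicity as binomial proportions, and a proportion with a CI for ISRs is the same reading. The protocol's background ISR figures are per subject, and where Protocol 9.4.2 means events over person-time it uses a qualified term, the exposure-adjusted incidence rate. This stands in part: the bare term is ambiguous, so an outright departure from the protocol is not proven. But the only event rate the SAP defines (8.2.7, 11.5.4) counts events over person-time and is kept apart from the rate that counts subjects, so the per-subject reading needs to be stated.

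It is also fair to say that recurrence is not lost. Table 3.143, Figure 3.21, Table 3.144 and the AE counts by preferred term (SAP 8.2.4.1) would all reflect it. A reader might infer that the plan could report the two products as the same when their reaction burden differs widely. The documents do not support that: Step 5 shows the weekly display separating the arms. What is missing is an interval. Protocol 9.4.2 rules out inferential testing of safety variables, so no formal conclusion depends on one.

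A reader might also infer that an event rate by arm would test whether the liquid product's lower pH or larger volume causes more reactions. It would not. Protocol 6.1 gives the liquid placebo the same pH (5.9) and the same volumes (0.6 and 1.0 mL), and in this double-dummy design both arms receive an injection with those features every week.

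**Conclusion.** The point holds as a worthwhile, low-cost improvement. In SAP 8.2.2 the only ISR estimate with a stated CI is the once-per-subject proportion. It ignores repeat reactions and differing exposure, while the protocol, the SAP synopsis and the endpoint speak of rates. With 23 of 150 subjects affected, that estimate is fixed while the event rate varies eightfold as assumed reactions per affected subject go from 1 to 8. The size is illustrative only. It rests on the assumed recurrence counts, including the 1.5 versus 5 example with reactor numbers set equal by construction, and on a 15% figure borrowed from longer studies. The structural point, that the proportion cannot respond to recurrence, needs neither assumption.

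**What to change.** In SAP 8.2.2 and Table 3.141, add the on-therapy ISR event rate by arm with a 95% CI that allows for clustering within subject, from a negative binomial model with an exposure offset or from a robust variance. The denominator can be person-time (per 100 person-years, as in 11.5.3 and 11.5.4) or dosing visits from the Exposure page. Dosing visits are safer than individual injections, because SAP 6.6 describes that page as recording administration per visit and does not document a count by injector. Report the rate overall and for the 30 mg and 50 mg periods, and keep the subject proportion beside it. State in 8.2.2 what event rates means. If the sponsor intends subject proportions only, say so and record that choice in SAP 2.1.

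The cost is a few lines of SAP wording and one more table from data already collected. When reactions recur, the interval will be wider than a naive Poisson interval, as it should be. The primary analysis and the sample size do not change.

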8.2.3. Immunogenicity

Serum for antidrug antibody testing will be obtained from all subjects before administration of study treatment at Week 0, 2, 4, 8, 12, 16, 20, 24, 26/early withdrawal and at follow-up (if applicable), according to the Time and Events Table in [Appendix 2](#). The presence of anti-albiglutide antibodies will be assessed using a validated enzymelinked immunosorbent assay. The assay involves screening, confirmation, and titration steps (tiered-testing approach). Confirmed positive samples will be titrated to obtain the titre of antibodies and tested for GLP-1 and albumin cross-reactivity, as well as for albiglutide neutralizing activity. Samples positive for both anti-GLP-1 antibodies and drug neutralizing antibodies may be tested for GLP-1 neutralizing activity.

Anti-albiglutide antibody results will be analyzed by treatment arm, visit, and study period for the safety population. For subjects with positive anti-albiglutide antibody results, the number and percentage with positive albiglutide neutralizing antibody results, positive anti-GLP-1 antibody results, and positive anti-albumin antibody results will be provided separately at each assessment. The 95% confidence intervals for the proportions of the positive immunogenicity results will be calculated using exact binomial method, assuming a simple binomial distribution. Antibody titers will be summarized using descriptive statistics. Individual immunogenicity data, including antibody titers, will be listed for each subject.

Additionally, in the case of severe allergic reactions that include anaphylaxis, angioedema, or other severe potential hypersensitivity reactions, three 1-mL serum samples should be obtained for immunogenicity testing (within 24 hours of the event if possible) and sent to the central laboratory for immediate distribution to a contracted testing facility for specific immunological testing (albiglutide specific IgE and other tests,

as appropriate) A follow-up serum sample will be collected 8 weeks after the final dose of study treatment in the case of early withdrawal from the study. For subjects who have discontinued study treatment or subjects who have completed the 26 week treatment period, but do not consent and/or are not eligible to participate in the 26 week extension study (Study 204682), if baseline antibody levels or a reduction in titer are not achieved by the follow-up visit then additional samples for immunogenicity testing may be obtained every 30 days following the follow-up visit until baseline antibody levels, or reduced titres, are achieved. Subjects eligible for the extension study (Study 204682) will have immunogenicity samples taken as specified in protocol 204682.

The immunogenicity data in the case of severe allergic reactions will be listed.

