Screening comprises determination of a cutoff value for drug-naïve T2DM subjects and identification of serum samples potentially positive for anti-albiglutide antibody.

Confirmation

Specificity of serum antibodies is confirmed by competing their binding to albiglutide immobilized on plates with excess albiglutide in solution. If the sample is still positive after the confirmation assay, the sample will be reported as positive and further analysis will be done by the titration and neutralizing antibody assay and other secondary assays.

Titration

Confirmed positive samples will be titrated to obtain a titer value of anti-albiglutide antibody.

Neutralizing Antibody Assays

The neutralizing antibody assays are cell-based reporter gene assays, which include screening, confirmation and titration assays. Albiglutide-neutralizing activity is measured by adding serum samples pre-incubated with a fixed concentration of albiglutide to GLP-1 receptor/CRE (cyclic adenosine monophosphate response element)-luciferase transfected cells and measuring luminescence intensity after 3 hours of incubation. Samples possessing neutralizing activity will generate a reduced signal and will be further tested in confirmation (specificity) assay if the generated signal is positive (i.e., below the assay's screening cutoff). Confirmed positive samples will be titrated to obtain a titer value of neutralizing anti-albiglutide antibody.

Immunogenicity Testing Report

The immunogenicity testing report will include the incidence of immunogenicity, incidence of neutralizing antibodies and the antibody titers (binding and neutralization to albiglutide). Cross-reactive antibodies to GLP-1 and HA will be discussed.

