11.12. Appendix 12: Sample Size Considerations

11.12.1. Sample Size Assumptions

[figure not shown]
[figure not shown]
This study will randomly assign approximately 150 subjects to each of the 2 treatment groups (liquid drug product and lyophilized drug product) in a 1:1 ratio, for a total of approximately 300 subjects. Eligible subjects will be stratified by age (<65 or ≥65 years of age), weight (<90 kg or ≥90 kg), and background antidiabetic therapy (diet and exercise or stable dose of metformin).

With 133 subjects in each of the 2 treatment groups, the study will provide 90% power to demonstrate non-inferiority for HbA1c change from baseline, assuming a non-inferiority margin of 0.4%, an expected treatment group difference of 0.0%, and a common standard deviation of 1%, using a 2-sample, 1-sided t test with significance level of 0.025. Power was calculated using PASS [Hintze, 2013]. Assuming that 13% of subjects will be withdrawn early or will be lost to follow-up; therefore, approximately 150 subjects will be randomized in each treatment group.

The non-inferiority margin of 0.40 was selected based on the expected effect of the albiglutide lyophilized drug product as active control. Results from two HARMONY Phase III studies (subset of GLP112756 and GLP112753) for the comparison of the control albiglutide lyophilized drug product versus placebo were used in selecting the non-inferiority margin. The two studies are similar to the current study in terms of the population and the design; subjects were either on diet and exercise or metformin background therapy and received 30 mg of albiglutide then up-titrated to 50 mg albiglutide. The 95% confidence interval from the 2 Harmony studies for HbA1c change from baseline at week 24 for albiglutide lyophilized drug product difference from placebo is (-1.04, -0.75). The conservative effect in terms of the difference from placebo for HbA1c change from baseline at Week 24 for albiglutide lyophilized drug product versus placebo is 0.75% (M1 =0.75%, as defined in Guidance for Industry: Non-Inferiority Clinical Trials [FDA, 2010]). M2, calculated as 50% of M1 is 0.375 (approximately 0.4). The margin of 0.40% that should be met in this trial will preserve at least 45% of the effect of the comparator and it is below M1.

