3.143.	Safety		On-therapy Injection Site Reaction over Time		
3.144.	Safety		Summary Characteristics of On-therapy Injection Site Reactions		
3.151.	Safety		On-therapy and Post-therapy Liver Events Identified by a Customized MedDRA Query		
3.161.	Safety		On-therapy and Post-therapy Pancreatitis and Pancreatic Cancer		
3.162.	Safety		On-therapy and Post-therapy Adjudicated Pancreatitis Events		
3.171.	Safety		On-therapy and Post-therapy Atrial Fibrillation and Atrial Flutter Adverse Events		
3.181.	Safety		On-therapy and Post-therapy Pneumonia Adverse Events Reported by the Investigator		

Safety : Tables					
No.	Population	IDSL / TST ID / Example Shell	Title	Programming Notes	Deliverable [Priority]
3.182.	Safety		On-therapy and Post-therapy Pneumonia Adverse Events Identified by a Customized MedDRA Query		
3.191.	Safety		On-therapy and Post-therapy Diabetic Retinopathy Adverse Events		
3.201.	Safety		On-therapy and Post-therapy Appendicitis Adverse Events		
3.211.	Safety		On-therapy and Post-therapy Malignant Neoplasm Adverse Events Identified by a Customized MedDRA Query		
Lab Assessments					
3.221.	Safety		Change from Baseline in Hematology by Visit		
3.222.	Safety		Change from Baseline in Chemistry by Visit		
3.223.	Safety		Hematology Values of Clinical Concern by Visit		
3.224.	Safety		Chemistry Values of Clinical Concern by Visit		
3.225.	Safety		Liver Function Tests of Clinical Concern by Visit		
3.226.	Safety		Shift in Hematology by Visit		
3.227.	Safety		Shift in Chemistry by Visit		
3.228.	Safety		Urinalysis by Visit		
Vital Signs					
3.231.	Safety		Change from Baseline in Vital Signs by Visit		
3.232.	Safety		Vital Signs of Clinical Concern by Visit		
3.233.	Safety		Shift in Vital Signs of Clinical Concern by Visit		
[ECG]					
3.341.	Safety		Change from Baseline in ECG Values by Visit		
3.342.	Safety		ECG Values of Clinical Concern by Visit		

Safety : Tables					
No.	Population	IDSL / TST ID / Example Shell	Title	Programming Notes	Deliverable [Priority]
3.343.	Safety		Overall ECG Interpretations by Visit		
3.344.	Safety		Shift in ECG Values of Clinical Concern from Baseline to Week 26		
3.345.	Safety		ECG QTcF and QTcB Results of Notable Abnormalities at any time post-baseli		
Immunogenicity					
3.351.	Safety		Positive Immunogenicity Results for Anti-Albiglutide Antibody Positive Subjects by Visit		
3.352.	Safety		Positive Immunogenicity Results for Anti-Albiglutide Antibody Positive Subjects by Therapy Phase		

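### Percentages and confidence intervals for neutralizing, anti-GLP-1 and anti-albumin antibodies are based on antibody-positive subjects only; add the incidence among all exposed and sampled subjects

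*SAP*

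**What the plan says.** SAP 8.2.3 analyzes anti-albiglutide antibody results by arm, visit and study period in the Safety population. For the follow-on assays it narrows the base: "For subjects with positive anti-albiglutide antibody results, the number and percentage with positive albiglutide neutralizing antibody results", then anti-GLP-1 and anti-albumin results, are given separately at each assessment. Exact binomial 95% intervals are attached to the proportions positive. Titers are summarized and individual data are listed.

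SAP 11.14.5 lists two immunogenicity tables. Table 3.351 is titled "Positive Immunogenicity Results for Anti-Albiglutide Antibody Positive Subjects by Visit"; Table 3.352 has the same title by therapy phase. Figure 3.61 plots the number and percentage positive over time, for anti-albiglutide antibody only.

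On the protocol side, section 9.4.2 says immunogenicity will be evaluated by event rates with 95% CI. It also says that no inferential testing is done on safety variables. Appendix 7 describes a separate document: "The immunogenicity testing report will include the incidence of immunogenicity, incidence of neutralizing antibodies". It states neither a denominator nor a split by arm.

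**The concern.** Immunogenicity is one of the two safety questions that this comparability trial singles out, because protocol 2.1 says non-clinical work cannot predict it. A reader will want to know how many exposed subjects on each product develop neutralizing or cross-reactive antibodies, and how large that rate could plausibly be.

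A percentage among ADA-positive subjects does not answer this. The base is formed after randomization by a response to the product, so the arms being compared are no longer the randomized arms. Numerator and denominator can rise together and leave the percentage unchanged. The base is also so small that the interval excludes very little. By contrast, SAP 8.2.2 reports injection site reactions, the other question singled out, as number and percentage of subjects by treatment group with a 95% CI.

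**Working it through.** **1. Arm size.** The documents give no sample size or precision figure for immunogenicity, so the arm size comes from the primary endpoint. SAP 11.12.1 states: "With 133 subjects in each of the 2 treatment groups, the study will provide 90% power to demonstrate non-inferiority for HbA1c change from baseline", with margin 0.4, true difference 0, SD 1 and one-sided alpha 0.025.

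- Normal approximation: n = 2 × (1.960 + 1.282)² × 1² / 0.4² = 131.3, so 132 per arm.
- Exact t-test power is 89.9% at 132 and 90.1% at 133, so 133 is reproduced.
- Dropout: 133 / (1 − 0.13) = 153, against a plan of approximately 150.

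Below, 150 treated and sampled per arm is assumed.

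**2. Expected ADA-positive subjects.** Protocol 2.1 gives 4.4% for the lyophilized product; protocol Table 2 gives about 5%. 150 × 0.044 = 6.6 and 150 × 0.05 = 7.5, so about 7 to 8 per arm are ever positive. Fewer will be positive at any one visit, because protocol 2.1 describes the antibodies as mostly transient.

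**3. Exact (Clopper-Pearson) intervals.** With x = 0 the upper limit is 1 − 0.025^(1/n). With x > 0 the limits are the 2.5% point of Beta(x, n − x + 1) and the 97.5% point of Beta(x + 1, n − x). Protocol 2.1 calls earlier antibodies non-neutralizing, so zero or nearly zero is the likely count.

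| Positive / base | Percentage | 95% CI |
|---|---|---|
| 0/3 (one visit, assumed) | 0% | 0 to 70.8% |
| 0/7 | 0% | 0 to 41.0% |
| 0/8 | 0% | 0 to 36.9% |
| 1/7 | 14.3% | 0.4 to 57.9% |
| 0/150 | 0% | 0 to 2.4% |
| 1/150 | 0.67% | 0.02 to 3.7% |

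Over an assumed ADA rate of 2% to 10% (3 to 15 positives), the upper limit for zero neutralizing runs from 70.8% to 21.8%.

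**4. Joint rise (hypothetical counts, lyophilized v liquid).**

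- Both double: the conditional percentage is 1/7 v 2/14, 14.3% in each arm. Incidence is 1/150 v 2/150, 0.67% v 1.33%.
- Both triple: 2/7 v 6/21, 28.6% in each arm. Incidence is 2/150 v 6/150, 1.3% v 4.0%.

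**5. What the other planned output would show.** In the doubling case, ADA incidence is 7/150 = 4.7% (1.9 to 9.4%) v 14/150 = 9.3% (5.2 to 15.2%), and the counts beside the percentages read 1 v 2.

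**6. What the all-exposed base does not achieve.** Fisher's exact test gives p = 1.0 for 1/150 v 2/150 and p = 0.28 for 2/150 v 6/150. Power to separate ADA rates of 4.4% and 8.8% with 150 per arm (two-sided 5%) is about 33%. These are illustrations; no such test is planned.

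**The case against.** A reader might infer that the plan reports these assays as percentages alone, and that a product raising both ADA and neutralizing antibodies would show no difference. The documents do not support that. SAP 8.2.3 plans numbers beside the percentages, analyzes ADA by arm in the Safety population and lists individual data; Figure 3.61 plots ADA positivity. With 1:1 arms, a joint rise would show in the counts and in ADA incidence.

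Four further points deserve weight:

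- **The conditional percentage follows the assay design.** Only confirmed-positive samples go on to the secondary assays, so it is a fair description of the antibodies found. This stands, and is why the row should be kept.
- **The denominators are partly inferred.** They come from one sentence and two table titles; no table layout is shown. That is so, but sentence and titles agree, and nothing in the SAP points to an all-exposed base for these assays.
- **Appendix 7 may supply the incidence elsewhere.** It may, but it promises no arm split, stated denominator or interval, and it lies outside the SAP displays.
- **The analysis is descriptive.** No decision rule depends on these rows, and a reader could divide the counts by N. This lowers the priority. It does not remove the gap: the reader would have to compute the intervals, and the right N is not simply the Safety total. Protocol Table 5, the schedule for subjects who stop investigational product, has no immunogenicity sample, so the number sampled falls over the visits.

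**Conclusion.** The point holds in a limited form. The planned percentages and intervals for the three secondary assays rest on a post-randomization subset of about 7 subjects per arm. That percentage cannot show a proportional joint rise. In the likeliest case, no neutralizing antibodies, its interval reaches 41%, while the same data over 150 exposed subjects would bound the incidence at 2.4%. The two limits describe different quantities; the second is the one that protocol 9.4.2 and Appendix 7 point to, and no SAP display gives it.

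The planned output as a whole does not conceal a difference, and the change would not let the trial detect one. This is a cheap improvement to a descriptive analysis of a named secondary objective. The figures assume 150 treated and sampled subjects per arm and an ADA rate of 4.4% to about 5%; the neutralizing counts in the scenarios are hypothetical.

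**What to change.** In SAP 8.2.3 and Tables 3.351 and 3.352, add for each of the three assays n/N, percentage and exact 95% CI by arm.

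- **N:** Safety subjects with at least one evaluable post-baseline sample; in by-visit rows, the subjects sampled at that visit.
- **Cumulative row:** any positive result on therapy, most naturally in Table 3.352.
- **Negatives:** state that sampled subjects found ADA-negative count as negative on the secondary assays, because their samples are not tested further.
- **Existing row:** keep the percentage among ADA-positive subjects as a secondary descriptive line, and amend the table titles to cover both bases.

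The cost is SAP wording and a few extra rows in two tables. No new samples, assays or data are needed.
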